6.3 Data Collection

[figure not shown]
The following data will be collected:

Pre-operative/Baseline

- Name
- MRN
- Age
- Race
- Ethnicity
- Gender
- Height
- Weight
- BMI
- Telephone number
- Email address
- Knee Extension (degrees)
- Knee flexion (degrees)
- History of depression
- History of anxiety
- History of diabetes
- History hyperlipidemia
- History of tobacco use
- Widespread pain inventory
- · Duration of preoperative opioid use
- Most recent intra-articular steroid injection in affected joint
- Statin use
- Gabapentinoid use
- Anticonvulsant use
- SSRI use
- Tricyclic antidepressant use
- SNRI use
- Presence of osteophytes on x-ray
- NRS pain score in operative knee at rest
- NRS pain score in operative knee with movement
- Worst NRS pain score in operative knee in past 24 hours
- Least NRS pain score in operative knee in past 24 hours
- PainDETECT questionnaire
- KOOS Knee survey
- Pain Questionnaire
- Quality of Life Questionnaire
- KOOS Physical Function Shortform

Surgical procedure (Intra-operative)

- Knee Extension (degrees)
- Knee flexion (degrees)
- Tourniquet time in OR

- Surgery start time
- Surgery end time
- Length of surgery
- Surgeon
- Anesthesiologist
- ASA
- Blood draw completed? (Y/N; Why)
- Blood draw arterial or venous?
- Blood drawn from side with IV? (Y/N; Why)
- Plasma aliquoted and stored? (Y/N)
- Blood hemolyzed (red plasma)? (Y/N)
- Joint fluid aspirated? (Y/N; Why)
- Did the joint fluid contain blood? (Y/N)
- Joint fluid aliquoted and stored? (Y/N)
- Was midazolam administered? (Y/N; dose)
- Was propofol administered? (Y/N)
- Was 4 mg dexamethasone administered intravenously? (Y/N)
- Was fentanyl administered? (Y/N; dose)
- Was ketorolac administered? (Y/N; dose)
- Was ketamine administered? (Y/N)
- Was dexmedetomidine administered? (Y/N)
- Did the patient receive neuraxial anesthesia with an epidural for postoperative pain? (Y/N)
- Did a patient receive an adductor canal/subsartorial saphenous nerve block containing ONLY local anesthetics (no additives)? (Y/N)
- Was topical TXA administered? (Y/N; dose)
- Was IV TXA administered either intraoperatively or postoperatively? (Y/N; dose)

Post-Operative

- Knee Extension (degrees)
- Knee flexion (degrees)
- Average daily opioid and non-opioid pain medication consumption
- Statin use
- Gabapentinoid use
- Anticonvulsant use
- SSRI use
- Tricyclic antidepressant use
- SNRI use
- NRS pain score in operative knee at rest
- NRS pain score in operative knee with movement
- Worst NRS pain score in operative knee in past 24 hours
- Least NRS pain score in operative knee in past 24 hours
- PCS questionnaire
- PainDETECT questionnaire
- KOOS Knee survey
- Pain Questionnaire

- Quality of Life Questionnaire
- KOOS Physical Function Shortform
- Blood draw completed? (Y/N; Why)
- Blood draw arterial or venous?
- Blood drawn from side with IV? (Y/N; Why)
- Plasma aliquoted and stored? (Y/N)
- Blood hemolyzed (red plasma)? (Y/N)
- Was IV TXA administered either intraoperatively or postoperatively?
 (Y/N; dose)
 - Changes from default TKA postop protocol? (Y/N)
- Was there escalation from the postoperative pain protocol at any point during the inpatient stay? (Protocol: PCEA with standard settings, oxycodone or hydrocodone 510 mg q4h prn, PO or IV acetaminophen standing dose or prn, meloxicam. E.g., needing higher doses, needing extra days of PCEA, addition of a new class of medication such as gabapentinoids, etc.) (Y/N)
 - Epidural PCA Placement Time
 - Epidural PCA Removal Time
 - Time Epidural PCA Was in Place
 - Did the patient require IV PCA? (Y/N)
 - Time to ambulation of 40 feet (with or without assistance)
 - Time to independent transfer (sitstand)
 - Postoperative joint stiffness? (Y/N)
 - Was manipulation performed for joint stiffness?
 - Postoperative persistent pain? (Y/N)

7.0 STATISTICAL ANALYSIS

- Proposed analysis: Firth's penalized likelihood logistic regression
- Interim analysis planned: No
- Alpha level: 0.05
- Beta or power level: 0.8
- Primary outcome variable estimate (mean +/- s.d. for continuous outcome, frequency/percentage for categorical variable): An estimated 10% of TKR patients will develop persistent postoperative pain (defined as NRS pain ≥ 4 with activity in the operated joint at 6 months postoperatively)
- Number of groups being compared: 1
- Effect size or change expected between groups: It is estimated that a one-standard deviation increase (an estimated 2.6 pg/ml [1]) in intraoperative joint fluid TNFalpha level will be associated with 2.49 times the odds of developing persistent postoperative pain.
- Resulting number per group: Estimating an R 2 of 0.3 if TNFalpha were regressed on model covariates (i.e., model covariates would explain 30% of

the variability in TNFalpha level), a total of 150 patients will need to be enrolled to detect an odds ratio of 2.49.

 Total sample size required: To account for 10% postoperative exclusions, we will enroll a total of 165 patients. 179 patients enrolled

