	Placement Time, Epidural PCA Removal Time, Time Epidural PCA Was in Place, Did the patient require IV PCA? (Y/N), Time to ambulation of 40 feet (with or without assistance), Time to independent transfer (sitstand), Postoperative joint stiffness? (Y/N), Was manipulation performed for joint stiffness?, Postoperative persistent pain? (Y/N).	
Statistical Analysis:	 Proposed analysis (e.g., student's ttest, ANOVA, chisquare, regression, etc.): Firth's penalized likelihood logistic regression Alpha level: 0.05 	
	Beta or Power level: 0.8	
	 Primary outcome variable estimate (mean +/ s.d. for continuous outcome, frequency/percentage for categorical variable): An estimated 10% of TKR patients will develop persistent postoperative pain (defined as NRS pain ≥ 4 with activity in the operated joint at 6 months postoperatively) 	
	 Number of groups being compared (use 1 for paired analysis within the same subjects): 1 	
	Effect size or change expected between groups: It is estimated that a onestandard deviation increase (an estimated 2.6 pg/ml [1]) in intraoperative joint fluid TNF-alpha level will be associated with 2.49 times the odds of developing persistent postoperative pain.	
	 Resulting number per group: Estimating an R 2 of 0.3 if TNFalpha were regressed on model covariates (i.e., model covariates would explain 30% of the variability in TNFalpha level), a total of 150 patients will need to be enrolled to detect an odds ratio of 2.49. 	
	Total sample size required: To account for 10% postoperative exclusions, we will enroll a total of 165 patients. 179 patients enrolled	

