While little is known about the contributions of inflammation and oxidative stress to the pathology of OA, even less is known about their contribution to adverse outcomes after arthroplasty. This study aims to define the incidence and characteristics of persistent postoperative pain and joint stiffness after TKA in patients with severe OA. This study also aims to explore demographic and medical factors as well as inflammatory pathways associated with the development of persistent postoperative pain and joint stiffness. Persistent postoperative pain may occur in as many as 2040% of patients (1), and clinical risk factors may include severity of preoperative pain (2), severe early postoperative pain and psychological factors, such as depression, anxiety, and pain catastrophizing (3). There is growing evidence that cytokines and adipokines are associated with OA severity, progression, and associated pain severity. Rodent studies have associated a number of cytokines, including tumor necrosis factor (TNF)alpha, interleukin (IL)1\(\beta\), IL6, IL10, nerve growth factor and calcitonin generelated peptide, to OAassociated pain syndromes, including inflammatory pain and central sensitization (4,5). IL1β and IL18 levels in joint fluid have been associated with OA severity and progression in humans (6), and serum IL15 levels have been shown to correlate with pain severity in patients with OA (7). In patients with knee OA, TNFalpha in synovial fluid is associated with total Western Ontario and McMaster Osteoarthritis Index (WOMAC) scores and each of its three subscales (8). In patients with OA scheduled to undergo knee arthroplasty, low levels of adiponectin, high levels of leptin, and low adiponectin/leptin ratios in synovial fluid have been associated with

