After samples are collected, aliquots of blood, plasma and joint fluid will be frozen and stored for future analyses. PAXgene tubes will be stored for future RNA analyses. Sample analysis: Once enrollment is complete, joint fluid and plasma samples will be analyzed for TNFalpha and other cytokine and chemokine levels by the CTSC at Cornell using 30plex panels from Mesoscale. Adiponectin and leptin levels will also be assessed using Mesoscale assays. In addition, fresh blood samples will be processed for cellular and molecular analyses of inflammatory and related pathways using methods potentially including FACS and/or CytoF, RNA analyses, and protein analyses (e.g., assessment of Rho associated protein kinase (ROCK) activity) to be conducted at HSS in the lab of [name], the precision medicine core facility at HSS and/or affiliated core facilities at WCMC/RU/MSKCC). In the event that blood work cannot be collected at the 6week visit (±2

[figure not shown]
weeks), blood work may be collected at the 3month postoperative visit. Sample Analyses which may be performed (on deidentified samples) by our coinvestigators, the precision medicine laboratory at HSS, affiliated core facilities at WCMC/RU/MSKCC, and/or outside facilities include: · Blood Cells: After blood is collected, composition of white blood cell differential (PMN, monocyte, lymphocytes) may be documented by flow cytometer and/or CytoF. Samples may then be sorted into granulocytes, PBMC, and platelet poor plasma, and cells viably frozen for future validation of RNAseq data. An aliquot of the PBMCs will be directly assayed for ROCK activation, immune cell subsets and T cell function. Another aliquot will be cultured to assess ROCK activation and T cell function after stimulation by measuring molecules such asIRF4, IRF5, IRF8, IBP/Def6, SWAP70, ROCK1, ROCK2, and signaling molecules involved in responsiveness to activation stimuli. Samples may be then subjected to QPCR, Western blotting, immunofluorescence / immunohistochemical analysis, ELISA, FACS or other laboratory analysis to investigate the expression/function of the signaling components that might be implicated in OA and poor postarthroplasty outcomes. If deemed necessary CD4+ T cell purification will be performed, after which the cells will be either left unstimulated or stimulated.

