6.2 Postoperative Protocol

Pain and Function:

Depression, anxiety, pain at multiple sites, age, and sex have been shown to be associated with pain severity. Demographic information, psychological and medical history, and assessment of pain at multiple sites (using the Widespread Pain Inventory) will be collected or performed at enrollment. Because pain catastrophizing scale (PCS) scores are also associated with pain severity, the PCS will be administered on postoperative day (POD) 2. Furthermore, the following scales will be used to assess pain type and severity at enrollment and at 4 weeks (±3 days), 3 months (±1 week) and 6 months (±4 weeks) postoperatively. If patients initiate rescheduling of the postoperative phone calls, the surveys can be administered outside of the time window. If necessary, patients will be texted with their permission to schedule phone calls or surveys may be emailed to them via REDCap.

- 1. Numerical rating scale (NRS) pain scores (at rest, with movement, worst pain, least pain)
 - 2. The PainDETECT scale a validated measure of neuropathic pain
- 3. The KOOS questionnaire (Symptoms, Pain, Stiffness and Quality of Life subscales) and KOOS Physical Function Shortform a commonly utilized measure of pain and function in patients with knee OA NRS pain scores will also be collected on POD 1 and 2. Attainment of physical therapy goals will be recorded by research assistant on each inpatient day. In the OR, knee flexion and extension measurements will be made via visual assessments with the aid of a goniometer by the surgical team after anesthesia induction. At 6 months following enrollment, patients who developed postoperative joint stiffness and/or persistent chronic postoperative pain will be identified. Postoperative joint stiffness will be defined as ROM≤95 degrees at the 6week (±2 weeks) surgical followup in the postoperative clinic. Persistent postoperative pain will be defined as NRS≥4 with activity in the operated joint at 6 months postoperatively.

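### Do the unnamed covariates in the primary TNF-alpha model put the 5% error rate at risk?

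*Combined protocol and SAP*

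**What the plan says.** The primary analysis is a single line in Section 7.0: "Proposed analysis: Firth's penalized likelihood logistic regression". The sample size rests on an adjusted effect. Section 7.0 gives "Estimating an R 2 of 0.3 if TNFalpha were regressed on model covariates", and both it and the synopsis explain that "model covariates would explain 30% of the variability in TNFalpha level". No section names these covariates, counts them or gives a rule for choosing them.

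The nearest text is Section 6.2, which explains why certain variables are collected: "Depression, anxiety, pain at multiple sites, age, and sex have been shown to be associated with pain severity". It then adds pain catastrophizing: "the PCS will be administered on postoperative day (POD) 2". Section 6.3 lists dozens of variables. None is designated as a covariate of the primary model.

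Section 1.0 links preoperative status to both sides of the primary hypothesis: "TNFalpha in synovial fluid is associated with total Western Ontario and McMaster Osteoarthritis Index (WOMAC) scores and each of its three subscales" on the exposure side, and "clinical risk factors may include severity of preoperative pain" on the outcome side. On timing, Section 6.1 says "Once enrollment is complete, joint fluid and plasma samples will be analyzed for TNFalpha".

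**The concern.** Two analysts could follow the plan and fit different primary models. Preoperative pain is a plausible confounder by the plan's own account, so including or omitting it changes what the TNF-alpha odds ratio means. Catastrophizing on POD 2 and early postoperative pain are measured after the joint fluid is drawn, so adjusting for them could remove part of the effect.

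About 16 events are expected (179 × 0.9 = 161 evaluable; 161 × 0.10 = 16.1), so each choice carries weight. If the covariates were settled once TNF-alpha and 6-month pain were both known, the 5% level might not hold, and readers could not tell the planned model from its alternatives. The R² of 0.3 also cannot be checked without a list.

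**Working it through.** **Inputs (Section 7.0).** Alpha 0.05 (sidedness not stated), power 0.80, incidence p = 0.10, odds ratio 2.49 per SD of TNF-alpha, R² = 0.3, stated n = 150, 10% exclusions, 179 enrolled.

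**1. The plan's own figure.** For one continuous predictor in logistic regression, n = (z₁₋α/₂ + z_power)² / [p(1−p)(ln OR)²] ÷ (1−R²).
- Two-sided: 7.849 / (0.09 × 0.8323) = 104.8; 104.8 / 0.7 = 149.7, so 150. This matches.
- One-sided: 82.5 / 0.7 = 117.9, so 118. This does not match, so the plan is two-sided.

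**2. Sensitivity to R².** The same formula gives 105, 117, 131, 150, 175 and 210 patients for R² = 0, 0.1, 0.2, 0.3, 0.4 and 0.5. With 161 evaluable, the largest R² that still meets the requirement is 1 − 104.8/161 = 0.35. Enrollment above the target of 165 therefore leaves some room around 0.3.

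**3. Error rate when TNF-alpha has no effect, n = 161.** Assumed, not in the documents: five independent normal covariates sharing R² = 0.3 equally (0.06 each), all acting on pain in the same direction. The test is the Firth penalized likelihood-ratio test at two-sided 0.05. Columns give the odds ratio for pain per SD of the covariate sum.

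| Model | OR 1.0 | OR 1.5 | OR 2.0 |
|---|---|---|---|
| All five (R² = 0.30) | 4.5% | 4.6% | 4.3% |
| Two of five (R² = 0.12) | 4.7% | 7.5% | 13.4% |
| None (R² = 0) | 4.9% | 12.3% | 27.7% |
| Most favourable of 32 subsets | 13.0% | 20.2% | 34.9% |

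With three covariates raising and two lowering pain (OR 2.0), the no-covariate figure falls to 5.9%.

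**4. A second simulation, n = 150.** Here the odds ratio is per SD of each covariate, with three or five covariates.
- All covariates included: 4.1% to 5.0% in every scenario.
- Most favourable subset, covariates unrelated to pain: 10.5% (three covariates), 12.3% to 13.5% (five).
- Most favourable subset at OR 1.3, 1.5 and 2.0: 16%, 29% and 57% (three); 27%, 43% and 71% (five).
- No covariates, same scenarios: 12% to 68%. Much of the excess is therefore confounding from under-adjustment, which selection only adds to.

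The two simulations agree on a common scale. Dividing ln OR by √5 turns 1.5 and 2.0 per SD of the sum into about 1.20 and 1.36 per covariate. For five covariates, the most-favourable-subset rate then rises smoothly: 13% (1.0), 20% (1.20), 27% (1.3), 35% (1.36), 43% (1.5).

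**5. An ordinary data-driven rule.** Keep covariates with univariable p < 0.10 for pain, then test TNF-alpha once (n = 150). Error is 3.4% to 3.7% if the covariates are unrelated to pain and 5.5% to 8.3% if they predict it. Late choice alone does not produce 13%.

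**6. Match to the plan.** Of the fixed models in step 3, only the full one has the R² of 0.3 that the plan describes, and it holds 4% to 5%. The rows with inflated error are under-adjusted models, or a search for the smallest TNF-alpha p-value. The documents call for neither.

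**The case for a change.** The strongest reply needs no selective reporting. If covariates predict pain in the same direction, simply omitting them gives 12% to 28% false positives, and nothing in Section 7.0 expressly forbids that model. With a true odds ratio of 2.49, the 32 models fail to agree on significance in 27% to 31% of trials. Writing a list would cost a few sentences, and every candidate is already collected.

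Part of this stands. The primary test is not fully prespecified, and R² = 0.3 is a planning estimate, so it does not bind the analyst to a model.

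The rest weakens on inspection. A model without covariates is not the one the study was sized for. The disagreement with a true effect comes largely from comparing models with different targets: the unadjusted model rejects in 89% to 98% of trials and the full model in 69% to 74%, a gap of 15 to 29 points. The full model's shortfall against 80% is a separate matter that naming covariates would not alter. Hypothesis 1 in Section 3.0 speaks only of association, so an unadjusted association would still be a real marginal one. No text proposes the POD 2 or early pain measures for this model. Nor would asking for a list supply a better model: the documents do not show which set is right. A shorter list is not clearly safer either, since two of five covariates did worse than all five.

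**Conclusion.** The omission is real, but no change to the plan follows. Nothing the plan states gives a wrong result when followed: 150 is correct at 149.7, and a covariate set of the kind described keeps the error at 4% to 5%. The larger rates are conditional worst cases. About 13% needs five candidates and a search over 32 subsets for the best TNF-alpha result. The 16% to 71% range also needs covariates that predict pain in one direction, and much of it is confounding. The number, strength and independence of the covariates, and the selection rule, are all assumptions from outside the documents.

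Analysts have what they need to fill the gap sensibly. Sections 1.0 and 6.2 identify the clinically relevant baseline factors, and standard practice avoids adjusting for variables measured after the exposure. Because Section 6.1 defers the TNF-alpha assay until enrollment ends, the model can be settled before exposure values exist. This is a missing detail of prespecification, not an error in a number or rule.

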3.0 STUDY HYPOTHESES

1. Elevated levels of TNF-alpha in joint fluid of patients with OA is associated with the risk of development of persistent postoperative pain after TKA.

- 2. Persistent pain (defined as NRS≥4 with activity in the operated joint at 6 months postoperatively) occurs in 10% of patients undergoing TKA for OA.
- 3. Joint stiffness (defined as range of motion [ROM] \leq 95 degrees measured at 6 \pm 2 weeks postoperatively) occurs in 7% of patients undergoing TKA for OA.
- 4. Distinct immune signatures (identified via protein analyses, immunohistochemistry, nanostring, RNA-Seq, fluorescence-activated cell sorting (FACS), and/or mass cytometry [CytoF]) are associated with the risk of developing persistent postoperative pain following TKA in OA patients.
- 5. Distinct immune signatures (identified via protein analyses, immunohistochemistry, nanostring, RNA-seq, FACS, and/or CytoF) are associated with the risk of developing joint stiffness following TKA.
- 6. Demographic profile, comorbidities, psychological factors, pain profiles, pre and postoperative stiffness and inflammatory profiles interact to determine attainment of PT goals and functional outcomes following TKA.

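### Does the stated 0.8 power at 150 patients fail because the plan's 10% is overall incidence rather than the event rate at mean TNF-alpha?

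*Combined protocol and SAP*

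**What the plan says.** Section 7.0 (Statistical Analysis), repeated in the Synopsis, plans Firth's penalised logistic regression of persistent pain at 6 months on joint fluid TNF-alpha. The planning inputs are "Alpha level: 0.05" and "Beta or power level: 0.8". The event rate is worded as "An estimated 10% of TKR patients will develop persistent postoperative pain", and Hypothesis 2 in section 3.0 likewise says that persistent pain "occurs in 10% of patients undergoing TKA for OA". The effect is set per "a one-standard deviation increase (an estimated 2.6 pg/ml [1]) in intraoperative joint fluid TNFalpha level", which "will be associated with 2.49 times the odds of developing persistent postoperative pain". An R-squared of 0.3 is assumed for TNF-alpha regressed on the model covariates. The result is that "a total of 150 patients will need to be enrolled to detect an odds ratio of 2.49", followed by: "To account for 10% postoperative exclusions, we will enroll a total of 165 patients. 179 patients enrolled".

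The plan does not name the sample-size formula, the sidedness of the test, the number of covariates or the distribution of TNF-alpha.

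**The concern.** The usual closed-form formula for logistic regression on a continuous covariate uses the event probability for a patient at the covariate mean. With an odds ratio as large as 2.49 per SD, that probability differs from overall incidence, because the logistic curve averages upwards over the spread of the covariate when events are uncommon. Both places that give the 10% describe overall incidence. If 10% was entered where a lower figure belonged, 150 is too few for 0.8 power under the model behind the formula.

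At stake is how a null result on Hypothesis 1 is read. The 0.8 is the only power figure for the primary question. If the true figure were nearer 0.75, the chance of missing the planned odds ratio would be about one in four rather than one in five.

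**Working it through.** **Inputs from section 7.0:** alpha 0.05; power 0.8; event rate 10%; OR 2.49 per SD, so ln(2.49) = 0.912; R-squared 0.3; exclusions 10%; 179 enrolled. The SD of 2.6 pg/ml cancels because the OR is per SD.

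**Assumptions not in the documents:** a two-sided test, the TNF-alpha distribution, the number of covariates, and 179 × 0.9 = 161 evaluable patients.

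**1. The plan's own figure.** n = (1.960 + 0.842)² / [P(1 − P) × (ln OR)²] / (1 − R²). With P = 0.10:

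7.849 / (0.09 × 0.832) / 0.7 = 104.8 / 0.7 = 149.7, the stated 150.

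A one-sided test gives 118 and omitting the R-squared adjustment gives 105, so the two-sided, adjusted form is the likely source.

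**2. Overall rate against rate at the mean.** For standard normal Z, solve E[expit(a + 0.912 Z)] = 0.10. This gives a = −2.507 and expit(a) = 0.0754. So 10% overall corresponds to 7.5% at the mean. In the other direction, 10% at the mean corresponds to 12.9% overall.

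**3. The same formula with P = 0.0754.** n = 193.3. Power is Φ(√[n × 0.7 × 0.0754 × 0.9246] × 0.912 − 1.960):

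- n = 150: 0.694
- n = 161: 0.725
- n = 179: 0.769

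**4. The planned analysis.** Simulated power of the Firth penalised likelihood-ratio test, 10% overall incidence, R-squared 0.3, 10,000 replicates per setting (null rejection rate 0.045):

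| TNF-alpha | Covariates | n = 150 | n = 161 | n = 179 |
|---|---|---|---|---|
| Normal | 1 | 0.734 | 0.779 | 0.811 |
| Normal | 3 | 0.734 | 0.763 | 0.799 |
| Normal | 6 | 0.713 | 0.740 | 0.792 |
| Lognormal, log-SD 0.3 | 3 | 0.834 | 0.857 | 0.893 |
| Lognormal, log-SD 0.6 | 3 | 0.868 | 0.891 | 0.918 |
| Lognormal, log-SD 0.9 | 3 | 0.839 | 0.862 | 0.894 |

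Further lognormal runs (log-SD 0.3 to 0.6) gave about 0.81 to 0.84 at 150 and 0.85 to 0.87 at 161. With normal TNF-alpha and 10% as the rate at the mean, power at 150 is about 0.8.

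Under normality, then, the closed form in step 3 is somewhat pessimistic for the Firth test at 161: 0.725 against 0.74 to 0.78. Analytic alternatives at 161 give 0.765 (score) and 0.797 (variance-corrected Wald).

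**5. Another route to 150.** If the information is evaluated under the null hypothesis, every patient has the same event probability. The overall rate and the rate at the mean then coincide, and P(1 − P) = 0.09 enters directly. The result is again 150, with 10% meaning exactly what the plan says. This is an approximation, and under normal TNF-alpha the power it delivers at 150 is still about 0.72.

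**6. Sensitivity to the other planning guesses.** With normal TNF-alpha and the closed form at n = 161, power reaches 0.80 if overall incidence is 12% rather than 10%, or if R-squared is 0.16 rather than 0.3. At 15% incidence it is 0.88 and at 20% it is 0.95. Section 1.0 cites persistent pain rates that read as 10% to 40% and 20% to 40%, so 10% is the lowest rate it cites.

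**The case for a change.** The best case for a change is that the formula match is too close to be chance, that the formula's P is not the quantity the plan describes, and that simulating the planned test gives about 0.8 at 150 under one reading of 10% and 0.71 to 0.73 under the other when TNF-alpha is normal. The plan records 179 enrolled but leaves its power statement tied to 150. A sentence naming the formula, the meaning of 10% and the assumed distribution would cost almost nothing.

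The conditional arithmetic stands, and so does the observation that these details are not written down. Three parts of the case do not stand:

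- The figure of 150 does not require the rate-at-the-mean reading (step 5), so the plan cannot be said to have entered the wrong 10%.
- The shortfall depends on normality, which the plan does not assume. A concentration cannot be negative and may well be right-skewed. Under the skewed distributions examined, 0.8 is conservative even at 150.
- Replacing 0.8 with a lower range would rest on normality, a chosen number of covariates and 161 evaluable patients. None of these is in the documents, and the sponsor's statistician could reasonably dispute each one.

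**Conclusion.** The concern does not call for a change. The stated inputs give the stated 150. For the Firth analysis at 10% overall incidence, power with 161 evaluable patients is about 0.74 to 0.78 if TNF-alpha is normal and about 0.85 to 0.89 if it is right-skewed. If all 179 were evaluable it would be about 0.79 to 0.82 under normality. The plan's 0.8 lies within the span of these figures.

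Even in the unfavourable case the gap at 161 is about 2 to 6 percentage points (0.80 − 0.78 to 0.80 − 0.74). Moving the assumed incidence from 10% to 12% closes it. With 179 already enrolled, no sample-size decision remains, and a null result will be judged from the estimated odds ratio and its confidence interval rather than from a planning figure. The unnamed formula and distribution are gaps in documentation, and filling them would alter no result.
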